3.7 Measures

Primary Exposure: Randomization arm – intervention or wait-list control – will be considered the primary predictor variable for all primary analyses and recorded on study enrollment forms. Because the degree of engagement with the intervention will vary by individual, we will also capture intervention dose on study monitoring forms as a secondary exposure measure for additional (per protocol) analyses.

Primary Outcomes: (Evaluation: Aims 1 & 2): HIV testing uptake will be defined as any clinical evidence or report of HIV testing in each interval. This includes multiple data sources: documented HIV testing at a study clinic, report of having attended a non-study clinic for HIV testing, or evidence of HIVST kit receipt with self-report of HIVST use and/or documented HIVST use by the PN during a group or individual navigation session. The primary PrEP use outcome measure is PrEP *persistence*, which is the PrEP measure utilized for sample size calculations. We will document *PrEP initiation*, defined as a participant filling their first PrEP prescription, through PrEP dispensing information in the national SICLOM database. However, because initiation does not imply continued use, we will focus analyses of PrEP use on *PrEP persistence* – or documented use at every interval, defined as sufficient pill dispensation for complete 3-month coverage with no more than 10 days uncovered in the period. Secondary outcomes, including PrEP *adherence* and uptake of other prevention services (harm reduction, STI care) are listed in Table 3, below.

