Mediators: Intersectional Stigma: We will include a comprehensive suite of stigma measures that will be examined together in mediation and moderation analyses (see Analysis section 3.8). To explore the concept of intersectional stigma, we will analyze potential interactions between the stigma domains. This reflects the concept of intersectionality as more than an additive process of multiple stigmatized identities, but where experiences of multiple types of stigma create a confluence of interlocking systems of oppression that act synergistically as barriers to prevention and cannot be meaningfully interpreted independently. We will include quantitative measures of internalized, anticipated, and enacted stigma in the following domains: gender-related stigma, race-related stigma, stigma related to sex work and substance use, HIV and PrEP stigma. Stigma resilience is operationalized as coping self-efficacy and healthcare empowerment in the context of anticipated

and enacted stigma. Comprehensive surveys will be conducted at enrollment, interim, and endline at 6-month intervals; we do not expect changes in stigma every 3 months (interval for outcomes monitoring).

Covariates: We will measure demographic and other individual, social, and structural barriers or facilitators to care to assess potential covariates and confounders in analyses.

Table 3: Primary and Secondary Measures

Domain	Instrument/measure	Data source	Frequency of data collection/extraction
PRIMARY EXPOSURE			
Intervention	Randomization arm	Enrollment/study records	Continuous during enrollment
PRIMARY OUTCOMES			
HIV testing	Binary: Tested (HIVST or at a clinic) in past 3-months	Clinical data extraction; study records (HIVST); self-report (testing)	Extracted bi-annually, Continuous, Monitoring visits (3-monthly)
PrEP initiation	Binary: Initiation of PrEP in past 3-months*	National data (SICLOM)	Extract quarterly
PrEP persistence	Binary: PrEP dispensed with 80 or more days covered in 3-months per dispensation records*	National data (SICLOM)	Extract quarterly
SECONDARY OUTCOMES			
Prevention and service uptake	Uptake of harm reduction services	Self-report	Monitoring visits (3-monthly)
	STI referrals and treatment	Clinical data extraction; Self-report	Extracted bi-annually, Monitoring visits (3-monthly)
	Condom use (consistent use with regular and occasional partners and clients)	Clinical data extraction; Self-report	Extracted bi-annually, Monitoring visits (3-monthly)

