Primary analyses for Aims 1 and 2. We expect HIV prevention outcomes to improve in the intervention arm relative to the control arm during the main trial phase. We hypothesize that, following the intervention, odds of HIV testing will be higher for intervention participants relative to control participants (Aim 1, Hypothesis 1). We also hypothesize that, following the intervention, the odds of PrEP initiation and persistence will be higher for the intervention group than for the control group (Aim 2, Hypothesis 2). Our primary interest is to estimate the marginal or population-average effects of intervention participation on these primary outcomes rather than the effect for a hypothetical average subject¹²⁶. Moreover, within-subject outcome correlations are considered nuisance parameters rather than quantities of interest to be modeled explicitly. Accordingly, generalized estimating equations (GEE) will be used for the primary analyses to test Hypotheses 1 and 2 using time-averaged comparisons of post-baseline (follow-up) measurements of intervention group with control group in the main trial phase. Alpha (α) will be set at .05 for these two planned comparisons. The alternating logistic

regression (ALR) approach implemented in SAS PROC GENMOD will be used to address the 3-level clustering of observations within participants and participants assigned to *Guerreiras* group leaders. This analysis will follow an intent-to-treat (ITT) approach by including all randomized participants. Further detail on the analytic model and secondary analyses, including secondary outcomes, intervention persistence, and intervention replicability, are included in Form E, Statistical Design and Power.

Primary Analyses for Aim 3. GEE will be used to test Aim 3 hypotheses that, following the intervention, relative to the control arm, intervention arm participants will have: 1) higher mean levels of resilience to anticipated stigma, 2) higher mean levels of resilience to enacted stigma, and 3) lower mean levels of internalized stigma. Analyses will follow the same ITT modeling approach as described above for Aims 1 and 2, except that a normal distribution and identity link will be employed to analyze continuous, normally-distributed stigma scores. These hypotheses will be tested via planned time-averaged comparisons of post-baseline measurements of the two arms in the main trial phase. These comparisons will be tested at $\alpha=.05$ per comparison.

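### PrEP initiation is listed as primary beside persistence, but the plan counts two primary comparisons and never says which PrEP result decides Aim 2

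*Combined protocol and SAP*

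**What the plan says.** Three places give initiation primary standing:

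- Table 3 (section 3.7) has three rows under its primary-outcomes heading: HIV testing, PrEP initiation ("Binary: Initiation of PrEP in past 3-months") and PrEP persistence.
- Hypothesis 2 (section 3.8, primary analyses for Aims 1 and 2) is that "the odds of PrEP initiation and persistence will be higher for the intervention group than for the control group". The text that follows refers to the outcomes of both hypotheses as primary.
- Aim 2 (section 2) names initiation and persistence together. Its list of secondary prevention outcomes does not include initiation.

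Three places point to persistence alone:

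- Section 3.7, Primary Outcomes, names persistence as the primary PrEP measure and the one behind the sample size. Initiation will be documented, but "because initiation does not imply continued use, we will focus analyses of PrEP use on" persistence.
- Section 3.8 states that alpha "will be set at .05 for these two planned comparisons".
- The statistical power paragraph of section 3.8 gives detectable differences for HIV testing (13 points) and persistent PrEP use (8 points), and none for initiation.

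The method sentence does not settle it: "generalized estimating equations (GEE) will be used for the primary analyses to test Hypotheses 1 and 2 using time-averaged comparisons". Hypothesis 1 holds one outcome and Hypothesis 2 holds two.

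**The concern.** Three listed primary outcomes do not fit two planned comparisons, and no decision rule links the two PrEP outcomes. Aim 2 could be judged on persistence alone, on both outcomes, or on either. These rules have different error rates and different power, and the choice could be made after the results are known.

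The practical risk is a trial that misses on persistence and reports initiation as a pre-listed primary success. Section 3.7 itself says that initiation does not imply continued use, so such a result would not carry the meaning that the plan attaches to its primary PrEP measure.

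**Working it through.** **1. The plan's own figures.** Inputs from section 3.8: 400 participants allocated 1:1, 25% attrition, alpha .05, power .80, four post-baseline measurements, control proportions .50 (HIV testing) and .05 (PrEP use).

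- Analysable: 400 × (1 − 0.25) = 300, or 150 per arm.
- Per-arm n for one measurement, two-sided: n = [1.96·√(2p̄(1−p̄)) + 0.842·√(p₁(1−p₁)+p₂(1−p₂))]² / (p₂−p₁)².
- HIV testing, .50 vs .63: n = 227.1. PrEP, .05 vs .13: n = 199.7.
- With four measurements, effective n per arm = 150 × 4 / [(1+3ρ)·DE], where ρ is the within-participant correlation and DE the design effect for navigator pairs.
- The stated differences therefore imply (1+3ρ)·DE = 600/227.1 = 2.64 for HIV testing (ρ = 0.55 if DE = 1) and 600/199.7 = 3.00 for PrEP (ρ = 0.67 if DE = 1).

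Both are attainable. They cannot be confirmed, because the documents give neither ρ nor the intraclass correlations, nor whether the test is one- or two-sided. What matters here is that the power work covers two tests, and the PrEP one is persistence.

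**2. Counting the tests.**

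| Source | Primary PrEP outcome(s) | Primary tests implied |
|---|---|---|
| Section 2, Aim 2 | initiation, persistence | 3 with HIV testing |
| Table 3 | initiation, persistence | 3 |
| Section 3.8, Hypothesis 2 | initiation, persistence | 3, or 2 if joint |
| Section 3.7, Primary Outcomes | persistence | 2 with HIV testing |
| Section 3.8, alpha sentence | not named | 2 |
| Section 3.8, power | persistence | 2 |

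**3. Aim 2 false-positive rate under each possible rule.** Each PrEP test is taken at two-sided .05. The correlation r between the two test statistics is not in the documents and is assumed from 0 to .9. Correlated cases come from simulated bivariate normal statistics with no true effect on either outcome.

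- *Persistence alone decides:* .05.
- *Both required:* at most .05. With no effect on either outcome it is .0025 at r = 0 and .030 at r = .9. Power is lower than for persistence alone unless initiation never fails when persistence succeeds.
- *Either suffices:* 1 − .95² = .0975 at r = 0; .091 at .5; .078 at .8; .071 at .9.

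**4. Cost of keeping either-or with an alpha split.** Hold the effective n implied by the 8-point difference (199.7 per arm) and test each PrEP outcome at .025. Power for persistence falls from .80 to .71, or the detectable difference rises from 8.0 to about 9.0 points. Keeping power at .80 needs 1.212 times the sample: 400 × 1.212 ≈ 485.

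**The case against.** The strongest reply is that section 3.7 already answers the question. Only persistence is ever singled out as the primary PrEP measure, it is the sample-size basis, and it fits both the count of two comparisons and the power paragraph. On that view Table 3, Aim 2 and Hypothesis 2 are merely loosely worded. This stands as evidence of intent, and the fix follows it. It does not remove the conflict: focusing the analyses on persistence does not say that initiation will not be tested as primary, Table 3 then lists it as primary, and no text calls it secondary.

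A second reply is that Hypothesis 2 joins the two outcomes with *and*, which can mean that both must succeed; Aim 2 error is then at most .05. That reading is open, but the plan does not state it, and it sits badly with a power calculation for persistence only.

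Third, section 3.8 sends further detail on the analytic model and on power to Form E, which is not in the documents. It may name the deciding test. The sections available would still contradict each other.

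A reader might go further and infer that the plan lets Aim 2 be claimed on either PrEP test. No text says so; either-or is one of three rules left open. A reader might also infer that initiation is the easier test. The documents give it no control rate, effect size or detectable difference. Section 3.7 defines it as the first prescription filled, so a participant can score in at most one of the four 3-month intervals. How that behaves in a time-averaged comparison is not shown.

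**Conclusion.** The inconsistency is real and should be corrected. The plan lists three primary outcomes, counts two comparisons, and has no rule for what decides Aim 2.

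The size is conditional. If the conflict stays and either PrEP test at .05 is accepted, Aim 2 carries about a 7 to 10% false-positive rate instead of 5%. This assumes two-sided tests at .05 each and test correlations of 0 to .9. Under the persistence-only or both-required reading there is no inflation, so the figure measures the risk of leaving the matter open and is not a property of a stated rule.

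A reader might also want to quote an error rate over all three listed outcomes. Most of that would come from testing two aims: HIV testing and persistence alone, each at .05, already give 1 − .95² = .0975 if independent. Whether .05 is per test or shared across Aims 1 and 2 is a separate ambiguity. Aim 3 specifies its level per comparison; Aims 1 and 2 do not. Making initiation secondary does not resolve that, so a three-outcome figure should not be used to size this point.

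**What to change.** Move PrEP initiation to the secondary outcomes in Table 3. Reword Hypothesis 2 and Aim 2 so that persistence alone is the primary PrEP outcome, and add initiation to the secondary outcomes named in Aim 2 and section 3.7. State in section 3.8 that the two planned comparisons are HIV testing and PrEP persistence. Check that Form E agrees. Aim 2 must change along with the table and the hypothesis, or a new mismatch replaces the present one.

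This costs wording only. Data collection, sample size and the stated power for persistence are unchanged. The downside is that initiation can no longer be claimed as a stand-alone primary result.

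If the sponsor wants initiation to stay confirmatory, state a fixed order: test persistence at .05, and test initiation at .05 only if persistence is significant. This holds Aim 2 at .05 and leaves the power for persistence intact. Splitting alpha between the two would also control the error, but at the loss of power or the larger sample shown in the working.

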3.3. Research Approach

3.3.a Research Design Overview. We will conduct a randomized controlled trial, where upon enrollment participants will be randomized to either the *Guerreiras* intervention or to a wait-list control condition, in which participants will also receive the *Guerreiras* intervention after a one-year waiting period. We chose a wait-list control to safeguard ethical treatment of participants by ensuring that a potentially impactful intervention will be available to all after a brief waiting period. Rolling enrollment of 400 participants will take place over one year, with the intervention initiating activities as participants are assigned to a *Guerreiras* group (8-10 participants); group assignment will occur as soon as sufficient participants are enrolled. *Guerreiras* includes five group sessions over the course of 6-8

weeks, led by two peer navigators (PNs). Following group sessions, PNs will provide six months of peer navigation to each participant to support HIV testing (clinic or HIVST), PrEP uptake and persistence, harm reduction and other behavioral prevention as indicated, or HIV care (if participant tests positive). Groups will reconvene for a reunion session 3 months into navigation services (see Intervention Design 3.4). Follow-up data collection for the main

Figure 2: Study Design

trial phase will be conducted every three months, with comprehensive interviewer-administered surveys conducted at enrollment (baseline), 6 months (interim survey), and 12 months (endline), with brief monitoring surveys at the 3-month visits (e.g. 3- and 9-months) to assess prevention uptake (HIV testing, PrEP use, etc; see Figure 2, Study Design). This results in four post-enrollment follow-up visits per participant to document regular prevention uptake and two visits to document changes in stigma measures during the main trial phase. Qualitative interviews will be conducted with 18 participants at two timepoints (36 interviews total) to provide context to our exploration of intersectional stigma and gender affirmation, including how intersectional stigma impacts engagement with *Guerreiras* and HIV prevention uptake, how gender affirming programming impacts intersectional stigma, and insight into psychosocial mechanisms of change over time.

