The second phase of the study, the delayed intervention phase, provides an opportunity for the control arm to receive the *Guerreiras* intervention and simultaneously to a) follow intervention arm participants for a further six months to assess the persistence of intervention effects, and b) replicate main trial findings utilizing wait-list control data. Wait-list control participants will be assigned to a *Guerreiras* group for initiation of the full intervention following the main trial and completion of their endline survey. HIV testing will be monitored through clinical records at partnering services, through PN forms on HIVST distribution, and through monitoring visits every 3 months. PrEP initiation and persistence will be monitored using the national medications dispensing system (SICLON), which is utilized in all public clinics. Dried blood spots (DBS) testing will assess drug levels among those on PrEP to measure of adherence and collected at clinic visits for PrEP dispensation. Comprehensive surveys measuring stigma domains will occur at 6-month intervals (see Measures 3.7).

3.3.b Study Setting and Population

Study setting. The proposed study will take place in the São Paulo metropolitan area in Southern Brazil in collaboration with the Santa Casa School of Medical Sciences (*Faculdade de Ciências Médicas da Santa Casa de São Paulo*). São Paulo is the largest city in Latin America, among the first to document HIV among LGBTI

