3.4.e. Peer navigator training: Our team of investigators is experienced in staffing, training, and supervising clinical and behavioral intervention trials. We will identify and intensively train twenty potential peer navigators (PNs). Among these, 16 will be selected based on fit for facilitating the intervention. All PNs will be trans women, half will be living with HIV and currently receiving HIV care, and half will be HIV-negative and utilizing HIV prevention tools. PNs will be paired to ensure mixed status navigation teams to provide role modeling for HIV prevention and treatment, as well as to address HIV-related stigma for those who seroconvert or avoid testing due to fear of a positive result. PNs will be identified through stakeholders, clinics, and CBO partners as well as through NUDHES, a successful approach for identifying PNs for the Trans Amigas project.

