The multi-week PN training will adapt detailed manuals we developed for facilitating the Sheroes group sessions and conducting peer navigation in Trans Amigas. For the group-level component, PNs will acquire skills in group facilitation through coaching, role plays, and mock sessions. HIV-related training content will include personalized HIV risk assessment, HIV test counseling (including HIV self-testing), PrEP, and HIV treatment. Stigma-related training content will include the concepts of intersectional stigma and gender affirmation, with a focus on the types of stigma targeted by the intervention (identity, social position, and barriers) and building stigma resilience through coping skills (e.g. coping with anticipated and enacted stigma) and empowerment. For the individual-level component, PNs will be trained on the role of a PN, providing support to participants in developing a personalized HIV prevention plan, fostering an alliance, and ethical behavior, including maintaining appropriate personal/professional boundaries. PNs will learn about interactions they will have with participants (e.g., in-person meetings, phone calls, text messages) and how to record them (see 3.6e for intervention monitoring), assessing participant needs, and strategies for addressing routine and more challenging barriers to prevention and care. To learn about potential resources for participants, PNs will tour trans-friendly service agencies in São Paulo, including the LGBT Citizenship Center, the Alcohol and Drugs Psychosocial Care Center, NGOs providing harm reduction support, the Racial and Intolerance Crimes Police Station, and the Social Assistance Reference Center. PNs will meet with the study coordinator weekly to conduct case conferences, receive support, and problem-solve. The study coordinator will have biweekly calls with investigators to discuss issues and strategize solutions. Refresher trainings will be conducted regularly to improve facilitation and navigation skills, to train new PNs if staff turnover occurs, and to address challenges.

3.5. Participant Eligibility, Recruitment, Randomization, Retention.

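### The primary GEE test names no small-sample correction, although about 8 navigator pairs, all in one arm, carry the intervention-arm variance

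*Combined protocol and SAP*

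**What the plan says.** - **Test.** Section 3.8 (Primary analyses for Aims 1 and 2) specifies GEE with a time-averaged post-baseline comparison of the arms. Alpha "will be set at .05 for these two planned comparisons". The clustering is handled by the alternating logistic "regression (ALR) approach implemented in SAS PROC GENMOD will be used to address the 3-level clustering of observations within participants", with participants nested under group leaders. The Aim 3 tests follow the same approach with an identity link.
- **Navigators.** Two peer navigators lead each group (3.3.a). Twenty are trained (3.4.e): "Among these, 16 will be selected based on fit for facilitating the intervention". Further, "PNs will be paired to ensure mixed status navigation teams".
- **Groups.** Each intervention participant joins a "group (8-10 participants); group assignment will occur as soon as sufficient participants are enrolled" (3.3.a).
- **Controls.** Wait-list participants are assigned to a "group for initiation of the full intervention following the main trial and completion of their endline survey" (3.3.a).
- **Power.** Section 3.8 lowers the effective sample size for correlation within navigator pairs, gives no ICC value, and states detectable differences of 13 points (HIV testing) and 8 points (PrEP).
- **Not in the supplied text.** There is no variance estimator, reference distribution, degrees of freedom or cluster count. Further model and power detail is referred to Form E, which was not supplied.

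**The concern.** The plan treats the navigator pair as the unit within which participants are correlated. In the main phase only intervention participants have a pair, so each control is a cluster of one. The 200 control clusters do not help with the other arm: its contribution to the variance is estimated from about 8 pair totals.

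With so few units two things go wrong in the same direction. The uncorrected sandwich is biased low, and a normal reference ignores how poorly the variance is estimated. Both primary tests and the Aim 3 tests would then reject a true null more often than 5%, and 95% intervals would cover less than 95%. Lowering the effective sample size for the ICC protects planned power. It does nothing for the size of the test.

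**Working it through.** **Inputs.** From the documents: α = .05 (two-sided assumed); 200 per arm (3.5.c); 16 navigators in pairs (3.4.e); four post-baseline measurements, control proportions .50 and .05, and 25% attrition (3.8). Derived: 16/2 = 8 pairs; 200/8 = 25 per pair randomized; 150/8 = 18.75 per pair analysed. Assumed, because not given: pair ICC 0 to .10 and the within-person correlation ρ.

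**The plan's detectable differences.** A single measurement needs about 228 per arm for .50 against .63 and about 200 for .05 against .13 (pooled two-proportion formula, 80% power). Four measurements multiply this by (1 + 3ρ)/4. The intervention arm is deflated by 1 + (18.75 − 1) × ICC.
- At ICC 0, 150 per arm yields 13 points if ρ = .55 and 8 points if ρ = .67.
- At ICC .01 the deflation is 1.1775, and the required ρ values are .48 and .59.
- At ICC .05 they are .28 and .36.

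The stated figures are therefore plausible but cannot be pinned down without ρ and the ICC.

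**Analytic check of test size.** Let s be the share of the variance of the arm contrast that comes from the intervention arm. With 8 pairs and 150 controls:
- Expected uncorrected variance / true variance: r = s × 7/8 + (1 − s) × 149/150.
- Satterthwaite df = 1 / [s²/7 + (1 − s)²/149].
- Type I error = 2 × P(t_df > 1.96√r).

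For s = .5: r = .934, df = 26.7, cut-off 1.894, type I error 6.9%. For s = .9: r = .887, df = 8.6, cut-off 1.846, type I error 9.9%. A higher ICC raises s.

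**Simulation under the null.** There were 20,000 runs per cell (Monte Carlo SE about 0.15–0.25 points). The ICC is the observed-scale correlation between two participants of the same pair; ρ was .3 and .6. Pairs were 8 × 25, or 6 of 27 and 2 of 19. PrEP was also run with 8 × 23, because Table 3 restricts it to those with indications. Data were complete or had monotone dropout reaching 25%. Working correlation was independence or nested-exchangeable, the latter a stand-in for ALR. Uncorrected sandwich, normal reference:

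| ICC | HIV testing (p = .50) | PrEP (p = .05) |
|---|---|---|
| 0 | 6.4–6.8% | 6.3–7.0% |
| .01 | 6.7–7.3% | 7.1–7.8% |
| .02 | 7.1–7.8% | 7.3–8.5% |
| .05 | 7.9–8.6% | 8.6–10.7% |
| .10 | 8.2–9.2% | 11.4–13.7% |

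Aim 3 (two continuous measures): 6.4–6.7% at ICC 0 and 7.3–8.9% at .02–.10.

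A separate simulation with ρ = .5 gave 6.7–6.9% (ICC 0) to 8.8–9.1% (ICC .10) for HIV testing, and 6.7–6.9% to 11.9–12.4% for PrEP. A rough check with a packaged GEE routine (600 runs, HIV testing, ICC .02) gave 7.8% uncorrected and 5.3% with a bias-reduced sandwich.

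**Alternatives, same 8 pairs.**

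| Method | HIV testing | PrEP, ICC up to .02 | PrEP, .05 | PrEP, .10 |
|---|---|---|---|---|
| Kauermann-Carroll, Satterthwaite t | 4.6–5.5% | 4.6–5.8% | 5.5–6.9% | 7.1–8.9% |
| Mancl-DeRouen, Satterthwaite t | 3.7–4.6% | 3.9–4.9% | 4.5–5.8% | 5.7–7.5% |

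For Aim 3 the two corrections give 4.8–5.5% and 4.1–4.7%. A generalized score test holds at ICC 0 (4.8–5.3% and 4.8–5.2%). For HIV testing it reaches 5.6–7.9% at .02–.10; for PrEP, 6.5–8.4% at .05 and 9.2–12.1% at .10.

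**If the group were the cluster.** Groups of 8–10 give 20–25 clusters. With 22, HIV testing is at 5.3–6.2%. PrEP is at 5.4–6.9% up to ICC .05 and 6.9–7.9% at .10.

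**The case against.** - **Form E.** The plan says where the further model detail is kept, and nothing supplied actually specifies an uncorrected sandwich or a normal reference. This stands as a limit: the finding is an omission in the supplied text, and the error rates are conditional on the usual large-sample inference. Section 3.8 does, however, give the method, software, alpha and clustering, so the inference rule belongs beside them.
- **The larger figures need an unusual null.** Participants are individually randomized. If the programme affects nobody, pairs induce no correlation and the ICC is near 0. An ICC of .05–.10 with zero average effect means some pairs help and others harm. This has force for the type I error, so the top of the range should not set the priority. The excess at ICC 0 remains, and for interval coverage under a real effect, differences between pairs are quite natural.
- **The power statement points to a small ICC.** Using the simulation's ICC definition, ICC .05 gives detectable differences of 15.0–16.6 and 10.2–11.5 points, against the stated 13 and 8. ICC .02 gives 12.8–14.8 and 7.8–9.2. This is fair, although the stated figures may describe only the favourable end of the plan's ICC range.
- **Eight is an inference.** The plan does not say that pairs stay fixed, and it provides for refresher sessions "to train new PNs if staff turnover occurs". The power section's ICC unit still favours the pair.
- **The exact analysis was not simulated.** ALR had a stand-in (range ends moved by at most about 0.3 points), and multiple imputation was not run. The decimals should be read accordingly.

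**Conclusion.** The concern holds. On the supplied text, the primary tests have no stated protection against a small number of clusters in one arm. Run with an uncorrected sandwich and a normal reference, they exceed the nominal 5% in every 8-pair scenario tried. The excess is modest at small ICCs: about 1.3–2.8 points at ICC 0–.01. It grows with the ICC, most for the rare PrEP outcome.

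This rests on 8 pairs (derived), on assumed ICCs and within-person correlations, and on Form E not already specifying a correction. It says nothing about how far the 13- and 8-point detectable differences would move. The change should be made before the data are analysed. Confidence is medium.

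**What to change.** Keep the population-average GEE and add to section 3.8:

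1. In the intervention arm the cluster is the navigator pair as first assigned; in the control arm it is the participant.
2. One bias-corrected sandwich, Kauermann-Carroll or Mancl-DeRouen, with a t reference and Satterthwaite degrees of freedom, for Aims 1, 2 and 3. Kauermann-Carroll is closest to 5% for HIV testing and Aim 3. Mancl-DeRouen is closer for PrEP at ICC .05–.10 and mildly conservative elsewhere.
3. A simulation check of that choice for PrEP, since neither correction fully restores 5% at an observed ICC of .10. A score test alone is not a substitute at ICC .05–.10.
4. A software procedure that supports the chosen correction.
5. The number of pairs, the ICC and its scale, the within-person correlation, how the effective sample size was lowered, and the 13- and 8-point differences restated under the corrected test.

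If Form E already contains this, bring the text into the plan.

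**Cost.** Analysis wording, code, one simulation and a restated power calculation; no change to design or sample size. Intervals widen. For HIV testing, Kauermann-Carroll with t is about 8% wider at ICC 0, 11–13% at .02 and 19–21% at .10. Mancl-DeRouen with t is about 12%, 17–19% and 27–29% wider. The detectable differences may be somewhat larger.
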